12.4 Collection and Recording of Adverse Events

Adverse events (including SAEs) will be collected from the time of consent until a subject completes study participation or until 30 days after he/she prematurely withdraws (without withdrawing consent) or is withdrawn from the study.

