5.2 Inclusion Criteria

Individuals who meet all of the following criteria are eligible for enrollment as study participants:

1. Subject must be able to understand and provide informed consent
2. Have diagnosis of EoE (based on consensus criteria)¹
3. Are aged 18 to 60 years
4. Have histologically confirmed active disease ≥ 15 eosinophils/hpf in the esophagus within 12 weeks of screening visit
5. Symptomatic (have experienced symptoms within the last month prior to enrollment)
6. PPI confirmation. (As a part of the diagnosis of active EoE, it must be demonstrated that acid reflux disease is not the primary cause of the participant's symptoms by documentation that the participant has been on a high dose of PPI (at least one dose, once daily) for at least 8 weeks prior to a diagnostic endoscopy of EoE without histologic resolution (i.e., ≥ 15 eosinophils/hpf). (Due to the variety of doses and various PPIs available, the dose will be confirmed adequate at the discretion of the PI.)
7. Have a negative urine pregnancy test at screening if of childbearing potential. Females of childbearing potential must have a negative urine pregnancy test (β -hCG) prior to enrollment into the study (i.e., at screening). These participants must agree to use adequate birth control measures (e.g., condom, oral/injectable/subcutaneous contraceptives, intrauterine device, or sexual abstinence) during the study and for at least one month after the last dose of study drug which will be documented in the source documents.

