9.7 End of 2nd treatment phase or Early Withdrawal (Week 16)

For those participants who have completed the phase 2 therapy or have withdrawn early from the study, the following procedures will occur:

- Measure vitals (blood pressure, heart rate, respiratory rate, temperature), height and weight
- Physical exam performed by a study clinician or qualified staff member
- Administer patient-reported outcome questionnaires
- Assess AEs
- Obtain up to 4 biopsies from the esophagus for research purposes (taken during SOC EGD)
 - One of these esophageal biopsies will be used for EDP
- Assess participant compliance with therapy (SGC) and concomitant medications
- Pregnancy Test (urine)
- Measure morning cortisol (serum, ~1 tsp, or 5 mL)
- Collect fluticasone from participant (for those on SGC)
- Collect participant compliance logs; dietary log or SGC log
- Research lab samples
 - Blood (6-10 mL) or saliva (1-2 mL) for future genetic testing may be collected at this visit (if not collected previously)
 - Obtain CBC with differential (2-3 mL)- IF a CBC with differential was obtained clinically as part of standard of care within the screening period, obtain the results from the standard of care CBC

If a participant withdraws from the study before completing 6 weeks of SGC or 6FED therapy in Phase 2, the end of treatment/early withdrawal visit should be conducted within one week of the participant's stopping therapy. Participants should stay on SGC or 6FED until results of biopsies are communicated to them. Following the receipt of their biopsy results, the participant will return to standard clinical care.

Should pregnancy occur during either phase of the study, dietary therapy and/or dosing of study medication will be discontinued and the participant will be withdrawn from the study. The pregnancy will be followed clinically to term.

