11.1 Participant Completion

Participant completion is defined by completion of the EGD at the end of Phase 1 and Phase 2 (for those who choose to continue into Phase 2); there are two levels of completion, those that complete Phase 1 and those that complete Phase 2.

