12.4.2 Recording Adverse Events

Throughout the study, the investigator will record adverse events and serious adverse events as described previously (Section 12.2, *Definitions*) on the appropriate AE/SAE CRF regardless of the relationship to study therapy regimen or study procedure.

Once recorded, an AE/SAE will be followed until it resolves with or without sequelae, or until the end of study participation, or until 30 days after the subject prematurely withdraws (without withdrawing consent)/or is withdrawn from the study, whichever occurs first.

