17.7 Study Completion

Before a study can be considered completed or terminated, the investigator must have the following data and materials:

- Clinical laboratory findings, clinical data, and all special test results from screening through the EOT visit (to 30 days after the last dose of study agent).
- CRFs properly completed by appropriate study personnel and reviewed and approved by the investigator.
- Copies of protocol amendment(s) and IRB approval/notification if appropriate.
- A summary of the study prepared by the principal investigator (an IRB/IEC summary letter is acceptable).

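### Adverse-event collection ends at the final EGD for completers but runs 30 days for withdrawals, leaving last-biopsy and post-steroid events without planned follow-up

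*Protocol*

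**What the plan says.** - **Collection window.** Protocol 12.4 starts collection at consent and continues it "until a subject completes study participation or until 30 days after he/she prematurely withdraws". For events already recorded, 12.4.2 stops follow-up at resolution "or until the end of study participation, or until 30 days after the subject prematurely withdraws", whichever comes first.
- **Completion.** Section 11.1: "Participant completion is defined by completion of the EGD at the end of Phase 1 and Phase 2". Section 4.2 instead ties Phase 1 completion in remitters to the central pathology (CRPC) review, which is targeted within two weeks of endoscopy.
- **Close-out data.** Section 17.7 requires laboratory, clinical and special-test data "from screening through the EOT visit (to 30 days after the last dose of study agent".
- **Contraception.** Section 5.2, item 7, asks for it "for at least one month after the last dose of study drug".
- **End of Phase 2.** Section 9.7 states "Participants should stay on SGC or 6FED until results of biopsies are communicated to them", but its list of procedures for the same visit includes "Collect fluticasone from participant (for those on SGC".
- **Procedure events.** Section 12.2.2 names bleeding and perforation from EGD biopsies as adverse events. Section 6.4.4 gives the same risks for the additional research biopsies.
- **Schedule.** The last adverse-event assessment is the end-of-treatment visit: week 6 for those who finish at Phase 1 and week 16 for Phase 2. Nothing follows.
- **SAP.** The Adverse Events section tabulates events occurring during Phase 1 and Phase 2 and compares percentages by Fisher's exact test. It does not say when a phase ends for this purpose.

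**The concern.** The period after the last procedure or dose is covered for people who leave early but not for people who do what the protocol asks. A biopsy complication that appears the day after a completer's final EGD falls outside collection on the 11.1 definition. So does an event shortly after the end of the SGC course, or a pregnancy that begins in the month for which contraception is required. An event still open at the final EGD is no longer followed. Section 12.2.1 lists possible adrenal suppression as an adverse event, and the second cortisol sample is drawn at the very visit that closes collection. At stake is the completeness of the safety record. The primary efficacy comparison is not affected.

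**Working it through.** The plan states no figure to reproduce. The check compares the sections and adds simple arithmetic.

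**1. Days of planned collection after the final EGD**

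| Participant | Sections | Days |
|---|---|---|
| Completer, completion = EGD | 12.4 + 11.1 | 0 |
| Completer, participation ends at CRPC review or results | 12.4 + 4.2 / 9.7 | about 14 (assumes the two-week target is met) |
| Premature withdrawal | 12.4 | 30, counted from withdrawal |
| SGC participant, close-out data | 17.7 | 30, counted from last dose |

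Both readings for completers fall short of 30.

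**2. Is there a contact that could fill the gap?** 30 / 7 = 4.3 weeks. A 30-day period would end near week 6 + 4.3 = 10.3 for those finishing at Phase 1 and week 16 + 4.3 = 20.3 for Phase 2. The schedule has no contact after week 6 for the former or after week 16 for the latter. The synopsis gives a maximum duration of 27 weeks. Screening plus the full schedule is already 12 + 16 = 28, so no follow-up period is built in.

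**3. Which biopsies are affected?** Participants who enter Phase 2 have adverse events assessed at week 10, after the Phase 1 EGD. The gap therefore concerns each participant's last EGD only.

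**4. When is the last SGC dose?** Section 9.7 has participants stay on SGC until results are communicated, and also has the drug collected at the end-of-treatment visit. On the first statement, dosing can continue after collection has closed. On the second, it stops at the visit. The 30 days in 17.7 have no clear starting date until these are reconciled.

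**5. How many participants?** Inputs from section 13.6: remission 45% on 1FED and 70% on 6FED; 68 per arm enrolled, 60 per arm before the drop-out allowance.

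- Completing at the Phase 1 EGD by remission, 68 per arm: 68 × 0.45 + 68 × 0.70 = 30.6 + 47.6 = 78.2, about 78 of 136.
- The same, 60 per arm: 27 + 42 = 69 of 120.
- 6FED non-responders eligible for SGC: 68 × 0.30 = 20.4, or 60 × 0.30 = 18. Phase 2 is optional, so about 18 to 20 is an upper guide.

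Non-remitters who complete finish either at the Phase 1 EGD (those who decline Phase 2) or at the Phase 2 EGD. Every completer's last biopsy thus lies at the edge of the window set by 11.1. These are counts of people, not of missed events. The documents give no event rate for the post-EGD period.

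**The case against.** Several points against the concern carry weight.

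- **17.7 is a close-out checklist.** It names clinical and laboratory data, not adverse-event collection, and counts from the last dose of study agent. This stands: the conflict is direct for SGC participants and not clearly present for diet-only completers.
- **Completers are not left without safety checks.** Adverse events are assessed through the end-of-treatment visit. Cortisol and pregnancy are tested there, low cortisol goes to the primary care physician (7.1.5), and pregnancies identified during the study are followed to conclusion (12.5.6). It would be wrong to read the plan as providing no follow-up at all. What is missing is planned study collection after that visit.
- **The EGDs are standard of care (6.5).** True, but the added research biopsies are not, and 12.2.2 itself lists EGD biopsy events under study-mandated procedures.
- **Delayed steroid harm is not documented.** Section 6.1 calls the short-term side effects reversible and links the other effects to longer or chronic use. The case therefore rests on the protocol's own 30-day figures, not on a known late effect.

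A reader might go further and infer that safety observation is longest in the least exposed and that SGC event rates are biased downward. The documents do not support this. In a 42-day phase, a participant who withdraws on day d is observed for d + 30 days, which is less than 42 whenever d is below 12. The SAP tabulates events during Phase 1 and Phase 2, so post-withdrawal events may not enter the tables at all. The 12.4 rule is the same in both randomised arms, and SGC is a non-randomised extension.

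**Conclusion.** The concern holds as a gap in safety collection and an inconsistency between sections. Completers have 0 days of planned collection after the final EGD under 11.1, or about 14 if participation ends at results and the CRPC target is met. Withdrawals have 30. The gap applies to every completer's last biopsy, including about 78 of 136 (69 of 120) expected to complete by remission at Phase 1. The conflict with 17.7, and the lack of any contact in the month of required contraception, concern the SGC group, for which at most about 18 to 20 would be eligible. These counts rest on the section 13.6 remission rates. Neither the number of missed events nor any distortion of adverse-event rates can be derived from the documents, and none is claimed. The point should be corrected because the remedy is small and uses a period the protocol already states.

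**What to change.** 1. Reconcile protocol 4.2, 9.7, 11.1, 12.4, 12.4.2 and 17.7 so that the end of participation, the last dose and the end of adverse-event collection are each defined once. The two statements in 9.7 on SGC after the final EGD must be reconciled by the sponsor; no view is taken here on which is right.
2. Collect adverse events, serious adverse events and pregnancies in completers and withdrawals to one common point, using the 30 days already in 12.4 and 17.7. Name the starting date explicitly, with wording that covers diet-only participants as well as those on SGC.
3. Add one closing phone call to the schedule, and adjust the stated study duration.
4. State in the SAP that the adverse-event tables use the same post-treatment window for completers and withdrawals.

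The cost is wording in six protocol sections and the SAP, one schedule column, and one short call per participant. No endpoint, sample size or treatment rule changes.

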12.4.1 Collecting Adverse Events

Adverse events (including SAEs) may be discovered through any of these methods:

Observing the participant.

Interviewing the participant

Receiving an unsolicited complaint from the participant.

In addition, an abnormal value or result from a clinical or laboratory evaluation can also indicate an adverse event, as defined in Section 12.3, Grading and Attribution of Adverse Events.

12.4.2 Recording Adverse Events

Throughout the study, the investigator will record adverse events and serious adverse events as described previously (Section 12.2, *Definitions*) on the appropriate AE/SAE CRF regardless of the relationship to study therapy regimen or study procedure.

Once recorded, an AE/SAE will be followed until it resolves with or without sequelae, or until the end of study participation, or until 30 days after the subject prematurely withdraws (without withdrawing consent)/or is withdrawn from the study, whichever occurs first.

12.5 Reporting of Serious Adverse Events and Adverse Events

12.5.1 Reporting of Serious Adverse Events to Sponsor DAIT/NIAID

This section describes the responsibilities of the site investigator to report serious adverse events to the sponsor via SAE CRF. Timely reporting of adverse events is required by 21 CFR and ICH E6 guidelines.

Site investigators will report to the DMCC (USF) and DAIT/NIAID all serious adverse events (see Section 12.2.4, Serious Adverse Event), regardless of relationship or expectedness within 24 hours of discovering the event.

For serious adverse events, all requested information on the AE/SAE CRF will be provided. However, unavailable details of the event will not delay submission of the known information. As additional details become available, the AE/SAE CRF will be updated and submitted. AE/SAE reports should be reviewed by the investigator.

Upon entry of a SAE, the DMCC created Adverse Event Data Management System (AEDAMS) will immediately notify the Study Chair, site PIs, the Medical Review Officer, and any additional agencies (if applicable- industry sponsor, CTEP, etc.) of any reported adverse events via email.

Serious adverse events: The NIH appointed Medical Review Officer (MRO) determines causality (definitely not related, probably not related, possibly related, probably related, definitely related) of the adverse event. The MRO [and, if applicable, sponsor] may request further information if necessary and possibly request changes to the protocol or consent form as a consequence of the adverse event. A back-up notification system is in place so that any delays in review by the MRO beyond a specified period of time are forwarded to a secondary reviewer. The Adverse Event Data Management System (AEDAMS) maintains audit trails and stores data (and data updated) and communication related to any adverse event in the study.

Non-serious expected adverse events: Except those listed above as immediately reportable, non-serious expected adverse events that are reported to or observed by the investigator or a member of his/her research team will be submitted to the DMCC in a timely fashion (within 20 working days). The events will be presented in tabular form and given to the MRO and RDCRN DSMB on an [observational- “annual” / interventional “bi-annual”] basis. Local site investigators are also required to fulfill all reporting requirements of their local institutions. The DMCC will post aggregate reports of all reported adverse events for site investigators and IRBs.

12.5.2 Reporting to the FDA

The study PI, [name], MD, PhD, holds the IND for this study. Each site will report SAEs in the DMCC system as defined above in section 12. The DMCC adverse event notification system will notify the IND sponsor. SAEs will be reported to regulatory authorities per 21 CFR 312.32 and institutional policy. All AEs will be tabulated by the DMCC and available to the IND sponsor on a monthly basis. Adverse events will be reported by the IND holder, in summary form, at the time of continuing annual review to the IRB, FDA, DSMB and the NIAID.

12.5.3 Annual Reporting

[name] (the IND holder) will include in the annual study report all adverse events classified as:

Serious, expected, suspected adverse reactions (see Section 12.2.2, *Suspected Adverse Reaction*, and Section

12.2.3, *Unexpected Adverse Event*).

Serious and not a suspected adverse reaction (see Section 12.2.2, *Suspected Adverse Reaction*).

Pregnancies not reported as serious adverse events.

Note that all adverse events (not just those requiring 24-hour reporting) will be reported annually.

12.5.4 Expedited Safety Reporting

This option, with 2 possible categories, applies if the adverse event is classified as one of the following:

Category 1: Serious and unexpected suspected adverse reaction [SUSAR] (see Section 12.2.2, *Suspected Adverse Reaction* and Section 12.2.3, *Unexpected Adverse Event* and 21 CFR 312.32(c)(1)i).

The sponsor must report any suspected adverse reaction that is both serious and unexpected. The DAIT/NIAID shall report an adverse event as a suspected adverse reaction only if there is evidence to suggest a causal relationship between the study drug and the adverse event, such as:

A single occurrence of an event that is uncommon and known to be strongly associated with drug exposure (e.g., angioedema, hepatic injury, or Stevens-Johnson Syndrome);

One or more occurrences of an event that is not commonly associated with drug exposure, but is otherwise uncommon in the population exposed to the drug (e.g., tendon rupture);

An aggregate analysis of specific events observed in a clinical trial (such as known consequences of the underlying disease or condition under investigation or other events that commonly occur in the study population independent of drug therapy) that indicates those events occur more frequently in the drug treatment group than in a concurrent or historical control group.

Category 2: Any findings from studies that suggests a significant human risk

The sponsor must report any findings from other epidemiological studies, analyses of adverse events within the current study or pooled analysis across clinical studies or animal or *in vitro* testing (e.g. mutagenicity, teratogenicity, carcinogenicity) that suggest a significant risk in humans exposed to the drug that would result in a safety-related change in the protocol, informed consent, investigator brochure or package insert or other aspects of the overall conduct of the study.

[name] (the IND holder) shall notify the appropriate health authorities, the FDA, central IRB and all participating investigators of *expedited Safety Reports* within 15 calendar days; unexpected fatal or immediately life-threatening suspected adverse reaction(s) shall be reported as soon as possible or within 7 calendar days.

12.5.5 Reporting of Adverse Events to IRBs/IECs

Adverse events, including expedited reports, will be reported by CCHMC, in a timely fashion to the central IRB in accordance with applicable regulations and guidelines.

12.5.6 Pregnancy Reporting

The investigator shall be informed immediately of any pregnancy in a study subject. A pregnant subject shall be instructed to stop taking study medication. The investigator shall counsel the subject and discuss the risks of continuing with the pregnancy and the possible effects on the fetus. Monitoring of the pregnant subject shall continue until the conclusion of the pregnancy.

The investigator shall report to the Data Management and Coordination Center (DMCC) and DAIT/NIAID all pregnancies within 1 business day of becoming aware of the event using the CRF. All pregnancies identified during the study shall be followed to conclusion and the outcome of each must be reported. The Pregnancy CRF shall be updated and submitted to the Data Management and Coordination Center (DMCC) when details about the outcome are available.

Information requested about the delivery shall include:

- Gestational age at delivery
- Birth weight, length, and head circumference
- Gender
- Appearance, pulse, grimace, activity, and respiration (APGAR) score at 1 minute, 5 minutes, and 24 hours after birth, if available
- Any abnormalities.

All pregnancy complications that result in a congenital abnormality, birth defect, miscarriage, and medically indicated abortion - an SAE shall be submitted to the Data Management and Coordination Center (DMCC) and DAIT/NIAID using the SAE reporting procedures described above.

12.5.7 Reporting of Other Safety Information

An investigator shall promptly notify the study sponsor ([name]) as well as the DMCC and DAIT/NIAID when an “unanticipated problem involving risks to subjects or others” is identified, which is not otherwise reportable as an adverse event. The DMCC will notify the central IRB.

12.5.8 Review of Safety Information

12.5.9 Medical Monitor Review

The DAIT/NIAID Medical Monitor shall receive monthly reports from the DMCC compiling new and accumulating information on AEs, SAEs, and pregnancies recorded by the study site(s) on appropriate CRFs.

In addition, the Medical Monitor shall review and make decisions on the causality and relatedness of the SAE and pregnancy reports received by the DMCC (See Sections 12.5.1, Reporting of Serious Adverse Events to DAIT/NIAID and 12.5.6, Pregnancy Reporting).

12.5.10 DSMB Review

The DMCC will provide the DSMB with listings of all SAEs on an ongoing basis, including quarterly reports of all SAEs. Furthermore, the DSMB will be informed of expedited reports of SAEs.

12.5.10.1 Planned DSMB Reviews

The NIAID Data Safety Monitoring Board (DSMB) shall review safety data at least yearly during planned DSMB Data Review Meetings. Data for the planned safety reviews will include, at a minimum, a listing of all reported

AEs and SAEs.

The DSMB will be informed of an Expedited Safety Report in a timely manner. An SAE which the Medical Monitor determines to be an unexpected safety risk will be sent to the DSMB immediately.

12.5.10.2 Ad hoc DSMB Reviews

In addition to the pre-scheduled data reviews and planned safety monitoring, the DSMB may be called upon for ad hoc reviews. The DSMB will review any event that potentially impacts safety at the request of the protocol chair or DAIT/NIAID. In addition, any occurrence of meeting one of the study stopping rules as described in Section 11.5 will trigger an ad hoc comprehensive DSMB Safety Review. After review of the data, the DSMB will make recommendations regarding study conduct and/or continuation.

